2 PROTOCOL DETAILS

2.1 Study Objectives

Primary Study Objective:

- To assess the efficacy of two Dysport doses (600 units [U] and 800 U), compared to placebo in reducing urinary incontinence (UI) from Baseline to Week 6 following the first investigational medicinal product (IMP) administration.

Secondary Study Objectives:

- To assess the efficacy of two Dysport doses (600 U and 800 U), compared to placebo in improving bladder diary measures, urodynamic and patient-reported efficacy endpoints following the first IMP administration, including assessing duration of effect.

Statistical Analysis Plan

Version: Final v1.0

September-2018

Ipsen Protocol No. D-FR-52120-223

000000146513

Date of Issue: 21-

Covance Study ID:

- To assess the efficacy of two Dysport doses (600 U and 800 U) in improving bladder diary measures and patient-reported efficacy endpoints following retreatment IMP administrations, including assessing duration of effect.
- To assess the safety of two Dysport doses (600 U and 800 U) for the treatment of UI due to neurogenic detrusor overactivity (NDO).

2.2 Overall Study Design

This is a Phase III, multicenter, randomised, double-blind, parallel group, placebo controlled study to assess the efficacy and safety of two Dysport doses (600 U and 800 U) administered to the bladder of adult subjects with NDO due to spinal cord injury (SCI) or multiple sclerosis (MS).

The target population is subjects with UI caused by NDO due to either SCI or MS, who have not been adequately managed with oral medication and who routinely require clean intermittent catheterisation (CIC) to manage their bladder function.

The study will include two treatment periods.

- A double-blind placebo controlled (DBPC) treatment, i.e. following Treatment 1 on Day 1 during which subjects receive a single IMP treatment administration of either
 - Dysport 600 U
 - Dysport 800 U
 - Placebo.
- A subsequent double-blind active treatment period, during which subjects can receive multiple active IMP retreatment administrations of either;
 - Dysport 600 U
 - Dysport 800 U.

Subjects who were randomised to receive Dysport at Treatment 1 (600 U or 800 U) will continue to receive the same dose for all subsequent treatments and those who were initially randomised to placebo will receive either 600 U or 800 U, depending on their allocated randomisation sequence (see next section).

The study contains two subsets:

- Urodynamic subset (planned ≥ 200 subjects)
 - o All subjects in this subset must have standardised urodynamics (as described in the Study Specific Urodynamic Manual) during Screening and at Week 6 following each study treatment
 - o Screening standardised urodynamics must confirm the presence of NDO
- Non-Urodynamic subset
 - o All subjects in this subset must have documented urodynamic proven NDO in the 12 months prior to Screening. If not, then urodynamics must be performed per local practice during Screening to confirm the diagnosis of NDO

Statistical Analysis Plan

Version: Final v1.0

September-2018

Ipsen Protocol No. D-FR-52120-223

000000146513

Date of Issue: 21-

Covance Study ID:

o Urodynamics will not be performed in the post-screening period in this subset

Screening

Screening period will last for up to 30 days, but can be extended in certain circumstances to obtain an appropriately and fully completed bladder diary or to obtain a valid bladder diary. Furthermore, where a urinary tract infection (UTI) occurs after completion of the bladder diary and impacts the ability to perform urodynamics, the time to Screening Visit 2 can be extended until the UTI is resolved. During the screening period, informed consent will be obtained and eligibility for study participation will be assessed. Subjects will complete a 7-day bladder diary, urodynamic assessment, patient-reported outcome questionnaires and have blood and urine samples taken.

Randomisation/treatment

The Treatment Visit (Day 1) should occur up to 14 days after the screening period, but can be extended until the UTI is resolved (where a UTI has occurred and impacts the ability to perform IMP administration). At the Treatment 1 visit on Day 1, subjects who meet all the eligibility criteria will be randomised (in a 2:2:1:1 ratio) to one of four treatment sequences:

Sequence	Subjects	1 st Treatment in DBPC Cycle	Subsequent retreatment(s) in Dysport Cycles (Dysport Cycle 1, Dysport Cycle 2, etc)
1	110 subjects	Dysport 600 U	Dysport 600 U
2	110 subjects	Dysport 800 U	Dysport 800 U
3	55 subjects	Placebo	Dysport 600 U
4	55 subjects	Placebo	Dysport 800 U

During the analysis of DBPC cycle, the two placebo containing sequences will be pooled into a single arm.

Randomisation will be stratified by;

- Aetiology of NDO (SCI or MS)
- Previous intradetrusor botulinum toxin type A (BTX-A) usage (BTX-A naïve vs. BTX-A non-naïve).

Follow-up (after IMP administration in DBPC cycle):

- Week 1 (Day 8) (telephone)
- Week 2 (Day 15) (clinic visit)
- Week 4 (Day 29) (telephone)
- Week 6 (Day 43) (clinic visit; primary timepoint)
- Week 12 (Day 85) (clinic visit; the retreatment could be requested by subject from this visit)
- Every 12 weeks (telephone visits; until retreatment received or end of study (EOS) at Weeks 104 to 116).

Statistical Analysis Plan

Version: Final v1.0

September-2018

Ipsen Protocol No. D-FR-52120-223

000000146513

Date of Issue: 21-

Covance Study ID:

Details of the procedures performed at each visit following the first treatment are shown in the schedule of assessments, [Appendix V](#).

Retreatment assessment

A subject may request retreatment with IMP at any time ≥ 12 weeks after their most recent study treatment.

The retreatment criteria are as follows:

- 1) Retreatment requested by subject;
- 2) More than 12 weeks (84 days) since the previous IMP administration;
- 3) CCI [REDACTED]
[REDACTED]
[REDACTED]
[REDACTED];
- 5) In the investigator's opinion it is safe and appropriate to provide retreatment.

A patient may only be retreated if eligible based on the study retreatment criteria. The bladder diary device/portal may provide an indication that the patient is within 30% of their Baseline (Screening) UI level, however to confirm eligibility a manual calculation can be performed by multiplying the weekly number of UI episodes on the screening bladder diary by 0.7. If the subject has a current number of weekly UI episodes greater than this calculated number then the subject is within 30% of their Baseline UI level and meets the retreatment criterion #3.

Example calculation:

- Study Baseline (Screening) number of weekly UI episodes = 28 episodes
 $28 \text{ episodes} \times 0.7 = 19.6$ (rounded up to 20)
- Subject is therefore eligible for retreatment if current weekly UI episodes are 20 or more.

Retreatment should ideally occur within 14 days of confirmation of eligibility for retreatment and can occur up to and including Week 104 following the first IMP administration of the first period.

Retreatment follow-up

Follow-up after each retreatment follows the same schedule as the first IMP administration (Treatment 1).

- Week 1 (Day 8) (telephone)
- Week 2 (Day 15) (clinic visit)
- Week 4 (Day 29) (telephone)
- Week 6 (Day 43) (clinic visit)
- Week 12 (Day 85) (clinic visit; the retreatment could be requested by subject from this visit)
- Every 12 weeks (telephone visits; until retreatment received or EOS at Weeks 104 to 116).

Details of the procedures performed at each Retreatment Follow-up Visit in the Dysport cycle are contained in [Appendix V](#).

End of Study Visit

The EOS Visit will take place between 104 and 116 weeks after the first IMP administration on Day 1. Subjects may receive study retreatment up to and including Week 104 and a minimum of 12 weeks of follow-up is required after each IMP administration. For those subjects completing the study, the EOS Visit will occur:

- At Week 104 after the first IMP administration, if it has been more than 12 weeks since the previous IMP administration.
- At Week 12 Retreatment Follow-up Visit, if the subject received their most recent IMP administration between Week 92 and Week 104 following their first IMP administration.

Early discontinuation

A subject who discontinues the study early should, if at all possible, be followed-up for at least 12 weeks following their most recent IMP administration and should attend the EOS Visit.

Duration of subject participation

104 weeks (24 months) to 116 weeks depending on the timing of final IMP administration.

2.3 Sample Size and Power

The sample size is based on the ability to detect a statistically significant treatment difference in the weekly number of UI episodes at Week 6 following the first IMP administration in the two Dysport arms (600 U and 800 U) compared to the placebo arm.

Assuming a weekly decrease of 21 UI episodes in each Dysport arm and a weekly decrease of 12 UI episodes in the placebo arm, with a common standard deviation of 20 UI episodes, 80% power, and an alpha of 0.025 (as testing of both the 600 U and 800 U doses vs. the placebo dose will be performed simultaneously), a sample size of 96 subjects per dose group (a total of 288 subjects) is needed. Dropout between randomisation and Week 6 (primary efficacy timepoint) is expected to be 10%, and thus a total of 318 subjects would be needed to be enrolled. However, in order to ensure that the development program will deliver adequate Dysport exposure data to meet ICH E1 guideline recommendations, a total of 330 subjects are planned to be randomised. Subjects who leave the study early will not be replaced.

Sample size calculations were performed in SAS Studio 3.6.

3 EFFICACY AND SAFETY VARIABLES

For the purpose of all analysis, the study baseline is defined as the last value available during screening or day of treatment visit prior to the first study IMP treatment administration (Treatment 1) i.e. prior to the DBPC Cycle. This study baseline will be used in analysis of the efficacy endpoints and the safety endpoints for all treatment cycles.

3.1 Primary Efficacy Endpoint

The primary efficacy endpoint is the mean change from study baseline in weekly number of UI episodes at Week 6 after the first IMP administration (Treatment 1).

3.2 Secondary Efficacy Endpoints

The secondary efficacy endpoints are divided into those that relate to parameters measured in the bladder diary, those measured by urodynamic filling cystometry and those that are quality of life measures. From these secondary measures, there are two that have been selected to be analysed as part of a hierarchical testing scheme see Section 3.2.1.

Bladder diary measures:

Mean change from study baseline to post-treatment timepoints in the following variables:

- weekly number of UI episodes (except for week 6 after Treatment 1 which is the primary efficacy endpoint)
- total daily urinary frequency (spontaneous void and CIC)
- daily spontaneous voiding frequency
- daily CIC frequency
- total 24-hour voided volume (spontaneous void and CIC)
- 24-hour voided volume (spontaneous void only)
- 24-hour voided volume (CIC only)
- total volume per void (spontaneous void and CIC)
- volume per void (spontaneous void only)
- volume per void (CIC only)

Proportion of subjects with:

- no episodes of UI (i.e. 100% improvement where continence is achieved)
- UI response at several levels (i.e. $\geq 30\%$ improvement, $\geq 50\%$ improvement, $\geq 75\%$ improvement)

Urodynamic filling cystometry measures (urodynamic subset only):

Mean change from study baseline to week 6 after Treatment 1 in the following variables:

- MCC
- MDP during storage
- Vol@1stIDC (subjects without a post-treatment IDC will have their Vol@1stIDC imputed from their MCC)
- maximum detrusor pressure at first involuntary detrusor contraction (PdetMax@1stIDC)

- end fill pressure (EFP)
- detrusor compliance (DC)

Proportion of subjects with:

- No IDCs (i.e. urodynamic cure is achieved)

Patient-reported outcome questionnaires:

Mean change from study baseline to post-treatment timepoints in the following variables:

- I-QoL total summary score
- I-QoL Score of domain: Avoidance and limiting behaviour
- I-QoL Score of domain: Psychosocial impact
- I-QoL Score of domain: Social embarrassment
- EuroQol 5-dimension 5-level (EQ-5D-5L): Total descriptive score
- EQ-5D-5L: self-rated health (VAS)
- modified patient global impression - improvement (mPGI-I) score (to be assessed at each timepoint without comparison to baseline)

Duration of effect following the first and subsequent treatments

- time to request retreatment
- time to eligibility for retreatment
- time between treatments.

Detailed definitions of all efficacy endpoints are presented in [Appendix II](#).

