**PAGE 91/139** 

Parameter	Unit	Calculation	
MCC	mL	Total instilled volume or instilled volume just prior to the terminal IDC	
		minus	
		incontinent volume	
MDP	cm H 2 O	Peak detrusor pressure during storage (filling) phase	
		minus	
		trace baseline pressure	
Presence of IDC(s)	N/A	N/A	
Vol@1stIDC	mL	Instilled volume when first IDC commences	
PdetMax@1stIDC	cm H 2 O	Peak detrusor pressure during first IDC	
		minus	
		trace baseline pressure	
EFP	cm H 2 O	Detrusor pressure at end of filling or just prior to the terminal IDC	
		minus	
		trace baseline pressure	
DC	mL/cm H 2 O	Change in bladder volume	
		divided by	
		change in detrusor pressure	
		(usually measured as MCC divided by EFP)	

Table 20 Urodynamic Parameters

DC=detrusor compliance; EFP=end fill pressure; IDC=involuntary detrusor contraction; MCC=maximum cystometric capacity; MDP=maximum detrusor pressure; PdetMax@1stIDC=maximum detrusor pressure at first involuntary detrusor contraction; Vol@1stIDC=volume at first involuntary detrusor contraction.

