6.2 Handling of Dropouts or Missing Data

6.2.1 Analysis Endpoints

6.2.1.1 Efficacy Endpoints

Refer to Section 3.1 and 3.2 for the list of primary and secondary efficacy endpoints and Section 3.2.1 for the list of secondary endpoints used in the hierarchical analysis.

Bladder diary: For data collected from the 7-day bladder diary, if there is 1 or 2 days with no data, the arithmetic means recorded (on the 5 or 6 days that do have events recorded) from the bladder diary parameters will be used for the days with no recorded bladder diary data. If there are more than 2 days of missing data, then the 7-day bladder diary data will be considered invalid.

Statistical Analysis Plan

Version: Final v1.0
September-2018

Ipsen Protocol No. D-FR-52120-223
000000146513

Date of Issue: 21-

Covance Study ID:

Primary efficacy endpoint: No imputation is planned for the primary analysis of the primary endpoint. A sensitivity analysis of the primary efficacy endpoint will be performed using multiple imputations (MI) for missing or invalid data (see Section 7.6.4.3).

Urodynamic secondary efficacy endpoints: All urodynamic data will be reviewed by independent central reviewers to determine the final values for the urodynamic parameters. Only the central reader urodynamic values will be used for analysis purposes. For the secondary efficacy endpoint of Vol@1stIDC, subjects who do not exhibit a post-treatment IDC after the first IMP administration will have Vol@1stIDC imputed using the recorded corrected MCC volume at that post-treatment visit.

Quality of life secondary endpoints: For I-QoL total summary score, in accordance with the I-QoL User's Manual (US English version, March 2013), if no more than three items are omitted, a normal arithmetic mean substitution will be computed for these omitted items and imputed to calculate the total summary score. If more than three items are omitted, then there will be no more imputation for those omitted items, and the total summary score will be missing. Similarly, this rule will be applied for each of the domain scores (avoiding and limiting behavior, psychosocial impact, and social embarrassment). These derived scores will be used for analysis, and the investigator recorded eCRF I-QoL total summary score, and each recorded domain score will only be listed.

The formula for the derived scale scores is as follows:

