7.6.6.2 Urodynamic Filling Cystometry Parameters

See Section 3.2 for list of urodynamic endpoints.

The summary tables for mean values at Week 6 and the mean change from study baseline for the DBPC cycle, and for the Dysport Cycles (i.e. Dysport Cycle 1, Dysport cycle 2 ...) will be presented using descriptive statistics for continuous endpoints. For each of the “mean change” at Week 6 urodynamic parameters, an ANCOVA model will be fitted using the “mean change” endpoint, as the response variable to obtain the p-value of treatment groups. The model will be the same as the sensitivity analyses for the primary efficacy endpoint in 7.6.4.2. The LSMEANS of the mean change from study baseline at Week 6 in each group with standard error, the difference of mean between the two treatment groups, the 95% CI of the difference and the p-value for treatment group will be presented.

Number and percentage of subjects with no IDC will be also summarised. A logistic regression model will be performed with “proportion of subjects” as the response variable. The model will include treatment group, and stratification variables.

Odds ratio, 95% CI of odds ratio, and p-value will be presented.

The SAS codes of logistic regression for reference are below.

CCI
[Redacted SAS code block]

In above codes, the variables are defined as:

Statistical Analysis Plan

Version: Final v1.0

Date of Issue: 21-

September-2018

Ipsen Protocol No. D-FR-52120-223

Covance Study ID:

000000146513

CCI

Line plots of the LS means of changes will be plotted for MCC, MDP, Vol@1stIDC. In addition, a bar chart for the proportion of subjects with no IDC at Week 6 will be plotted.

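### PdetMax@1stIDC has no value once contractions are abolished, yet the readable SAP tests it by ANCOVA with no rule for those subjects

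*SAP*

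**What the plan says.** - **Definition.** Protocol Table 20 (Section 7.3.2.1) calculates the parameter as "Peak detrusor pressure during first IDC" less the trace baseline pressure.
- **Endpoint.** SAP 3.2 lists "maximum detrusor pressure at first involuntary detrusor contraction (PdetMax@1stIDC" among the mean changes from study baseline to Week 6 after Treatment 1, and attaches no rule for subjects without a contraction.
- **Neighbouring endpoint.** The item just before it does have a rule: "subjects without a post-treatment IDC will have their Vol@1stIDC imputed from their MCC". Protocol 3.2.2.1 says the same. SAP 6.2.1.1, on missing urodynamic data, again names only that volume: "For the secondary efficacy endpoint of Vol@1stIDC, subjects who do not exhibit a post-treatment IDC after the first IMP administration will have Vol@1stIDC imputed". The substitute is the corrected maximum cystometric capacity (MCC) from the same visit.
- **Cure.** SAP 3.2 also has a responder endpoint, "No IDCs (i.e. urodynamic cure is achieved", which SAP 7.6.6.2 compares between arms by logistic regression.
- **Analysis.** For each mean-change parameter, SAP 7.6.6.2 says "at Week 6 urodynamic parameters, an ANCOVA model will be fitted using the" change as response, and adds: "The model will be the same as the sensitivity analyses for the primary efficacy endpoint in 7.6.4.2". That model has treatment, the two stratification factors and the baseline value. Least-squares mean difference, 95% CI and p-value are reported, and PdetMax@1stIDC is not exempted.
- **Status.** Protocol 9.6 leaves this parameter out of its ordered urodynamic list (MCC, maximum detrusor pressure (MDP) during storage, Vol@1stIDC, proportion with no IDC) and calls the remaining urodynamic endpoints exploratory. SAP 7.6.2 and 7.6.6 treat everything outside the two-endpoint hierarchy as exploratory.

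**The concern.** Subjects enter the urodynamic subset because screening urodynamics showed NDO, which the site judges by the presence of IDCs. The systematic loss of values therefore comes after treatment, and it falls on the subjects who responded best by the plan's own cure definition. An ANCOVA on those with a value is a comparison within a subgroup formed by outcome. If abolition differs between arms, randomisation no longer protects it.

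The missing-at-random statement in SAP 6.2.1.1 does not help. It refers to mixed models for repeated measures, whereas this is a single-visit ANCOVA. In addition, the value is not unobserved: it does not exist, because the contraction is gone.

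At stake is one exploratory mean difference and p-value. It could appear to contradict the MDP and no-IDC results only because responders were removed from it.

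**Working it through.** **1. The plan's nearest own figure.** No mean, SD or power is given for PdetMax@1stIDC. Protocol Table 21 gives 90% power for MCC with 200 subjects, difference 104.5 mL, SD 212.9 mL, alpha 0.05 (two-sided, Protocol 9.3). With both doses pooled against placebo (133:67):

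SE = 212.9 × √(1/133.3 + 1/66.7) = 212.9 × 0.150 = 31.9; power = Φ(104.5/31.9 − 1.96) = Φ(1.31) = 90.5%.

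The figure reproduces. It implies about 67 subjects per arm in Treatment 1 (200/3), which is used next.

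**2. Who stays in the ANCOVA.** No-IDC rates are not in the documents, so these are assumed. Retained = 67 × (1 − rate):

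| No-IDC rate, placebo / Dysport | Placebo kept | Dysport kept |
|---|---|---|
| 5% / 20% | 64 | 54 |
| 5% / 40% | 64 | 40 |
| 10% / 60% | 60 | 27 |

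**3. Direction and size, hand calculation.** Assume a baseline mean of 50 cm H2O, and a pressure reduction of 30% on Dysport and 5% on placebo in subjects who keep an IDC. If subjects lose their IDC at random, at rates p1 (Dysport) and p0 (placebo):

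- difference among those with an IDC = 50 × (0.70 − 0.95) = −12.5;
- difference with no IDC counted as 0 = 50 × [(1 − p1) × 0.70 − (1 − p0) × 0.95].

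At 5%/20%: 50 × (0.56 − 0.9025) = −17.1, so the ANCOVA shows 12.5/17.1 = 73%. At 20%/20%: 50 × (0.56 − 0.76) = −10.0, so it shows 125%.

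**4. Simulation.** 400,000 subjects per scenario; baseline mean 50, SD 25; the same reductions with log-scale noise of SD 0.35; ANCOVA on treatment and baseline. Four patterns of IDC loss were tried: at random, lower Week 6 pressure for given baseline first, low baseline first, high baseline first. All these inputs are assumptions. Ranges are over the four patterns:

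| No-IDC rate, placebo / Dysport | Effect, no IDC = 0 | Effect, no-IDC subjects dropped | Share retained |
|---|---|---|---|
| 5% / 20% | −15.6 to −18.7 | −10.8 to −13.3 | 59–85% |
| 5% / 40% | −21.0 to −26.5 | −8.2 to −14.1 | 37–67% |
| 10% / 60% | −26.1 to −29.3 | −5.8 to −15.7 | 22–60% |
| 20% / 20% | −8.6 to −11.0 | −10.8 to −13.7 | about 125% |

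If the drug works only by abolishing IDCs (5% reduction in both arms, unequal no-IDC rates), the dropped-subject estimate is about 0. The exception is when subjects with lower Week 6 pressure lose their IDC first, where it takes the wrong sign (+2.6 to +9.6).

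**5. Dependence on the target.** If the reference is instead the pressure subjects would have had with the IDC still present (about −12.5 here), the estimates in the first three rows fall on both sides of it (−5.8 to −15.7). Understatement therefore depends on counting no IDC as the best outcome, as well as on unequal abolition.

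**The case against.** **The rule may exist.** SAP 3.2 sends detailed endpoint definitions to Appendix II, which is not in the public text, and Protocol 7.3.2.1 sends urodynamic calculations to a separate manual. A reader might infer that the plan has no rule at all. The documents do not support that; they show only that each readable no-IDC rule is confined to Vol@1stIDC. This objection stands, and the request must allow for confirmation.

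**The direction is not fixed.** A reader might also infer that the result is always biased toward zero, or by a known fraction. It is not. Understatement needs more abolition on Dysport and a target that ranks no IDC best. Equal rates can inflate the estimate, and no single percentage can be defended from inputs the documents do not give. This stands too, but the selection on outcome does not depend on its direction.

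**The endpoint is exploratory and the effect is visible elsewhere.** MDP during storage does not need an IDC, and the no-IDC proportion has its own comparison. This limits the consequence, but a p-value from a selected subgroup would still be reported beside them.

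**Dropping the test departs from the protocol.** Protocol 9.3 foresees comparing each dose with placebo on the other secondary endpoints. One could keep the ANCOVA and label it as conditional on having an IDC, with counts per arm. That is more transparent, but its p-value would still not come from a randomised comparison. A rank analysis keeps all subjects with a Week 6 trace and keeps the planned comparison.

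**Conclusion.** The point holds in a limited form. On the readable text, subjects with urodynamic cure have no PdetMax@1stIDC at Week 6, no rule assigns them one, and a treatment-comparison ANCOVA is planned. Following that text gives a comparison selected after randomisation on outcome. This is conditional on Appendix II holding no rule.

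If Dysport abolishes more IDCs than placebo and no IDC counts as the best result, the pressure benefit is likely understated. In the 12 illustrative scenarios of that kind, 22% to 85% of the effect was retained, with every pressure input and no-IDC rate assumed. The actual size cannot be derived from the documents. No confirmatory claim is affected.

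**What to change.** Before database lock, amend SAP 6.2.1.1 and 7.6.6.2 in one of two ways, or confirm that Appendix II already has an equivalent rule:

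- **Descriptive.** Summarise PdetMax@1stIDC among subjects with an IDC, give the number with and without an IDC in each arm, and report no treatment p-value.
- **Rank-based.** Compare each dose with placebo by a rank analysis in which subjects with no IDC share the best rank. This keeps the protocol's dose-versus-placebo comparison.

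In either case MDP during storage remains the between-arm pressure comparison, since it is defined with or without an IDC.

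The cost is a few sentences, the loss of an unconditional mean difference in cm H2O for this one parameter, and an entry in SAP Section 8 (now marked not applicable) if the ANCOVA is dropped. No data collection changes. Settling the rule before unblinding avoids a post hoc choice.
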